# 1.1 Nonclinical Effects of Miransertib on Overgrowth Syndromes In Vitro

Antiproliferative activity of miransertib was assessed in 6 fibroblast cell lines derived from PROS patients with HHML (PIK3CA H1047R), CLOVES (PIK3CA H1047R), Macrodactyly (PIK3CA H1047R), and MCAP (PIK3CA H1047R, or PIK3CA E81K). These PROS fibroblast cell lines showed elevated AKT activity. Miransertib very potently inhibited proliferation of PROS fibroblasts in a dose- and time-dependent manner with less cytotoxicity as compared with rapamycin (mTOR inhibitor) and wortmannin (PI3K inhibitor). Treatment with miransertib markedly suppressed AKT and its downstream targets [Ranieri, C., et al 2018]. In addition, fibroblasts from the skin of a patient with FAO (PIK3CA H1047R) were evaluated and the results showed that miransertib inhibited both pAKT and pPRAS40 in a dose-dependent manner [Biesecker LG, Lindhurst MJ, Yourick MR, Dransfield DT 2014].

Miransertib was further evaluated in skin fibroblasts isolated from several patients with PS harboring the activating mutant of AKT1, AKT1 E17K mutation [Lindhurst, M. J., et al 2015]. pAKT levels were 7- to 29-fold higher and pPRAS40 levels were 9- to 20-fold higher in the mutation-positive SCC compared with mutation-negative SCC. Phosphorylation of AKT1 and its substrate PRAS40 and other AKT downstream targets was markedly reduced on treatment of miransertib for 24 hours at the concentration range of 31 to 500 nM. With as little as 30 nM of miransertib, pAKT levels were reduced to approximately half compared with the levels in untreated fibroblasts. At 500 nM of miransertib, all pAKT levels were nearly zero.

In an ex vivo study, pAKT levels were assessed in skin biopsies from 2 affected toes of one patient that were incubated in a culture medium for 96 hours at 37°C with or without serum in the presence or absence of miransertib at 125 nM [Lindhurst, M. J., et al 2015]. Phosphorylation of AKT was reduced from 4- to 7-fold for tissues incubated with serum and 9- to 27-fold for those in serum-free medium when miransertib was added. pPRAS40 levels were also reduced, though not as dramatically as pAKT.

In vitro antiproliferative activity of miransertib was also conducted in skin fibroblast cells from patients with PS (AKT1-E17K) and unaffected cells with wild type AKT1 were used as comparison [Lindhurst, M. J., et al 2015]. In both high (10%) and low (0.5%) serum, the mutation-positive cells were more sensitive to increased levels of miransertib than mutation-negative cells.

In summary, the PI3K/AKT pathway, which is dysregulated in overgrowth diseases such as PROS and PS, is frequently activated through mutations in PIK3CA or *AKT*. AKT1 mutation-positive cells and PROS cells treated with 625 nM of miransertib had 25% to 40%

reduction in cell viability (measured by AKT phosphorylation) compared with untreated cells, whereas in mutation-negative cells the reduction was 0% to 20% [Lindhurst, M. J., et al 2011]. A similar effect on PIK3CA-mutant cells was observed at miransertib concentrations of 1000 nM or below. The target tissue concentration required for adequate (50%-75%) inhibition of AKT phosphorylation is between 500 and 1000 nM; when concentrations were above 2500 nM, no additional effect on cellular proliferation was noted [Loconte DC, Grossi V, Bozzao C, Forte G, Bagnulo R 2015]. Thus, inhibition of AKT by miransertib is a rational approach for the therapeutic intervention in such diseases.

# 1.2 Toxicology of Miransertib in Animals

Miransertib was generally well tolerated in rats and monkeys up to doses of about 10 mg/kg/day. The toxicity profile in juvenile rats was not different from that of adult rats and there was no effect on male or female fertility in the juvenile toxicology study.

Based on the 4-week rat study, the  $STD_{10}$  of miransertib was determined to be 15 mg/kg/day when given daily via oral gavage. This correlates to a human equivalent dose of 90 mg/m²/day. Based on the 4-week monkey study, the HNSTD of miransertib was determined to be 10 mg/kg/day when given via oral gavage daily. This correlates to a human equivalent dose of 120 mg/m²/day. Hence, based on the ICH S9 guidance document, the Phase 1 starting dose was thus calculated to be 9 mg/m²/day or 13.5 mg/day. The initial starting dose of miransertib in humans was suggested to be 10 mg/day. The actual starting dose in the first-in-human study, ARQ 092-101, was 10 mg qod.

Dosing in the juvenile toxicity study in rats started on PND 21, correlating with a 2-year old child. Therefore, the results support the safe use of miransertib in pediatric patients down to 2 years of age. The weight of evidence indicates that miransertib is not mutagenic or aneugeic but is weakly clastogenic. Additional details can be found in the IB.

#### 1.3 Effects of Miransertib in Humans

#### 1.3.1 EFFECTS OF MIRANSERTIB IN ONCOLOGY

Safety, tolerability and preliminary efficacy of miransertib have been tested in more than 150 adult participants with advanced solid tumors and recurrent malignant lymphoma (ARQ 092-101 [NCT# 01473095] and ARQ 092-102 [NCT# 02476955]).

#### 1.3.1.1 ARQ 092-101

ARQ 092-101, A Phase 1 Dose Escalation Study of Miransertib in Adult Subjects with Advanced Solid Tumors and Recurrent Malignant Lymphoma, was an open-label, first-in-human of miransertib. A total of 120 participants were treated with miransertib monotherapy. miransertib was initially administered at 10 mg qod and dose escalated from 10 mg qd to 350 mg bid qw. Fifteen dose levels and 3 dosing schedules (continuous [up to 80 mg qd], intermittent [up to 270 mg qd one week on and one week off], and weekly [up to 350 mg bid qw]) were explored in this study. The MTD in adult cancer patients was determined to be 60 mg qd (approximately 30 mg/m²).

The most common reason for treatment discontinuation was radiological disease progression (76/120, 63.3%). Safety and PK details for the 28 participants who received continuous, daily dosing of miransertib are summarized below. This subset of ARQ 092-101 participants' data are the most relevant for Study ARQ 092-103. Additional details can be found in the IB.

The drug-related TEAEs at continuous dosing are shown in Table 1.

Table 1 ARQ 092-101 Drug-Related TEAE Reported by More Than 1 Participant With QOD/QD Dosing

Preferred Term	10 mg QOD (n=4)	10 mg QD (n=3)	20 mg QD (n=3)	40 mg QD (n=4)	60 mg QD (n=7)	80 mg QD (n=7)	Total (n=28)
Diarrhoea		1 (33.3)	1 (33.3)	1 (25.0)	1 (14.3)	2 (28.6)	6 (21.4)
Dry Mouth	1 (25.0)	1 (33.3)			1 (14.3)		3 (10.7)
Nausea		2 (66.7)		1 (25.0)	2 (28.6)	4 (57.1)	9 (32.1)
Stomatitis					1 (14.3)	1 (14.3)	2 (7.1)
Fatigue	1 (25.0)			1 (25.0)	1 (14.3)	1 (14.3)	4 (14.3)
Decreased Appetite				1 (25.0)		2 (28.6)	3 (10.7)
Hyperglycaemia					1 (14.3)	4 (57.1)	5 (17.9)
Dermatitis Acneiform						2 (28.6)	2 (7.1)
Dry Skin					1 (14.3)	2 (28.6)	3 (10.7)
Palmar-Plantar Erythrodysaesthesia Syndrome					1 (14.3)	1 (14.3)	2 (7.1)
Pruritus		1 (33.3)			2 (28.6)	2 (28.6)	5 (17.9)
Rash Maculo-Papular					2 (28.6)	3 (42.9)	5 (17.9)

ALT=alanine aminotransferase; AST=aspartate aminotransferase; QD=once daily; QOD=every other day Final study data; 07 Aug 2017

In Cohort 5, 80 mg qd, one of the first 3 participants experienced 2 DLTs (Grade 3 cardiac failure congestive and Grade 4 cardiomyopathy) and the Cohort was expanded to enroll 3 additional participants. After 2 more DLTs (Grade 3 maculopapular rash and Grade 3 hyperglycemia) were experienced by 2 other participants, qd dosing was reduced to 60 mg for Cohort 6. In Cohort 6, one of the first 3 participants experienced a DLT (Grade 3 increased AST) and the Cohort was expanded with no additional DLTs reported. The MTD was declared as 60 mg qd for the continuous dosing schedule.

#### 1.3.1.2 ARQ 092-101 Pharmacokinetics

Miransertib PK data for this study are available for all 28 participants treated with the continuous dosing. The mean  $C_{max}$  of miransertib ranged from 11 nM (10 mg qod dose) to 166 nM (60 mg qd dose) on Day 1 and from 29 nM (10 mg qod dose) to 787 nM (80 mg qd dose) on Day 15. The mean  $AUC_{0-24}$  of miransertib ranged from 163 h\*nM (10 mg qod dose) to 2217 h\*nM (60 mg qd dose) on Day 1 and from 489 h\*nM (10 mg qod dose) to 15212 h\*nM (80 mg qd dose) on Day 15. Miransertib accumulates with accumulation ratios ranging

from 2.9 (10 mg qd dose) to 7.2 (80 mg qd dose) for Cmax, and from 3.0 (10 mg qd dose) to 8.6 (80 mg qd dose) for AUC0-24. Due to the long elimination phase, the half-life of miransertib could not be accurately determined; however, it is estimated that the half-life of miransertib is in the range of 40 to 60 hours. Additional details can be found in the IB.

# 1.3.1.3 ARQ 092-102

ARQ 092-102 is an open-label, Phase 1b study of miransertib in combination with carboplatin plus paclitaxel, paclitaxel alone, or anastrozole for the treatment of selected solid tumors. As of the data cutoff date, 34 participants have been treated with miransertib. The most common miransertib-related TEAEs ( $\geq$ 20%) seen were diarrhea (35.3%), nausea (32.4%), fatigue (26.5%), maculopapular rash (26.5%), and decreased appetite (20.6%). Additional details can be found in the IB.

# 1.3.2 Effects of Miransertib in Overgrowth Diseases

# 1.3.2.1 A Phase 1 Dose-Finding Study of Miransertib in Children and Adults With Proteus Syndrome

Study 16-HG-0014 is an investigator sponsored study conducted under NIH IND 126197 [NCT02594215]). The primary endpoint of the study was to determine the biological effect of miransertib as measured by changes in pAKT levels in the affected tissue. Results from the study have been reported and are summarized below [Keppler-Noreuil, K. M., et al 2019].

In 5 of 6 participants, a reduction of 50% or greater of tissue pAKT levels was reported, and the primary endpoint of the study was met. The clinical efficacy measurements showed significant reduction in size of the CCTN in 2 participants at Cycle 12 by quantitative standardized photography. Three participants reported an improvement in pain as assessed by a standardized pain scale.

Overall, the drug was well tolerated with most AEs considered mild or moderate in severity. The most common drug-related AEs (observed in  $\geq$ 3 participants) were headache (66.7%) increase bone formation (66.7%), exostosis (66.7%), and pain in extremity (66.7%). Detailed summary of the safety data as reported by NHGRI Investigators' can be found in the IB.

#### 1.4 Conclusion

Based on the nonclinical data and observed activity in patients with PS treated with miransertib, this Phase 1/2 study was initiated to further explore the single agent activity of miransertib in patients with PROS and PS with known PI3KCA and AKT1 somatic activating mutations.

#### 2 INVESTIGATIONAL PLAN

PROS and PS are characterized by overlapping clinical features, but caused by different somatic activating mutations, PIK3CA and AKT1, respectively. The overgrowth can affect any organ and cause multiple disabling complications. The significant morbidity and mortality associated with these progressive disorders, together with their unique, single genetic mutations, make them good candidates for AKT/PIK3CA targeted therapies that were initially developed for oncology indications [Keppler-Noreuil KM, Rios JJ, Parker VE, Semple RK, Lindhurst MJ 2015] [Keppler-Noreuil, K. M., et al 2016].

As of 31-JAN-2019, a total of 15 PROS and PS patients with PIK3CA or AKT1 mutations have been enrolled and treated in Study 092 103.

The study includes 2 parts:

**Part A**: All participants enrolled before Amendment 6. Part A was designed to enroll 25 to 40 participants with PROS and PS.

**Part B**: All participants enrolled under Amendment 6 or higher. Cohort 1 will enroll PROS patients; Cohort 2 will enroll PS patients; Cohort 3 will enroll either PROS or PS patients who do not meet the eligibility criteria for Cohorts 1 or 2; and Cohort 4 will enroll patients previously treated with miransertib or currently receiving miransertib under Compassionate Use/Expanded Access.

Cohorts 1 and 2 were originally designed to determine the response rate of miransertib in a selected participant population, as measured by a change in target lesion size from baseline, using blinded independent central imaging review: volumetric MRI in PROS or cerebriform CCTN photography in PS.

# 2.1 Study Objectives

Under this amendment, the primary study objective for both Part A and Part B is to describe the safety and tolerability of miransertib in patients with PROS and PS, and further efficacy assessments have been removed. Part A was closed to enrollment after the approval of Amendment 6.

Amendment 7 will complete the final enrollment into the MOSAIC study and Compassionate Use/Expanded Access Program. In the future, patients will be transitioned to new miransertib programs.

# 2.2 Overall Study Design

This is an open-label, multicenter Phase 1/2 study of oral miransertib administered daily to patients with PROS and PS. The study will be conducted at up to 20 sites globally.

Part B will enroll approximately 65 participants with clinical diagnosis of PROS or PS with documented somatic PIK3CA or AKT1 mutations. Part B will be comprised of 4 Cohorts: Cohort 1 will enroll 20 participants with PROS with a measurable lesion by the study-

standardized volumetric MRI. Cohort 2 will enroll 10 participants with PS with measurable CCTN and pre-CCTN lesional area by the study-standardized photography. Cohort 3 will enroll approximately 25 PROS or PS patients who do not meet the eligibility criteria for enrollment in Cohort 1 or Cohort 2. Cohort 4 will enroll participants previously treated with miransertib or currently receiving miransertib Compassionate Use/Expanded Access.

In Part B (except Cohort 4), participants will receive miransertib at the 15 mg/m^2 qd dose level during the first 3 cycles, (a cycle of therapy is considered to 28 days). The dose will be increased to 25 mg/m^2 qd provided no clinically significant drug-related toxicity is observed. Participants who experienced miransertib-related toxicity or are unable to tolerate study medication during the first 3 cycles may be treated at lower doses.

Participants enrolled in Cohort 4 will continue treatment at the dose they were on at the time of enrollment, but their dose should not exceed the 25 mg/m^2.

For all participants, actual dose will be calculated using BSA, per the DuBois formula.

Participants will stay on treatment for up to 48 cycles.

To better understand the natural history of the disease of each individual participant, all participants will be asked to provide a detailed history of their disease, including prenatal and postnatal evaluations, and surgical operations, results of any functional tests performed before the study enrollment, and, when possible, imaging scans (eg, CT, MRI, US), photographs, and/or video recordings collected before study enrollment.

PIK3CA or AKT1 somatic mutations must be documented before enrollment. If the status is unknown, an archival or fresh tissue biopsy must be collected and tested for PIK3CA or AKT1 somatic mutations. For all enrolled participants, archival or fresh tissue biopsy should be collected and sent to the Sponsor or designee.

For Part B Cohort 1, 2, and 3, safety (eg, physical examination, vital sign measurements, clinical laboratory tests, use of concomitant medications, and collection of AE information) assessments will be performed at baseline, twice during the first cycle, and at each study visit thereafter. All clinical assessments and laboratory tests will be performed per the Schedule of Events [Table 3]

For Cohort 4, safety (eg, physical examination, vital sign measurements, clinical laboratory tests, use of concomitant medications, and collection of AE information) assessments will be performed every 3 months (Table 4). If clinically indicated, unscheduled laboratory tests and any clinical assessments or evaluations may be performed per the discretion of the investigator.

A single blood sample will be collected for CYP2D6 genotyping. The final clinical safety follow-up will be performed 30 days after the last dose of miransertib.

Miransertib is supplied as 5- and 10-mg capsules and should be swallowed whole (1 hour before or 2 hours after a meal). When medically necessary, the capsules can be opened and

sprinkled onto a small amount of sweetened semiliquid food (eg, apple sauce, chocolate syrup, or ice cream).

The study data and endpoints were reviewed by the Sponsor in 2020. It was concluded that the current data from this study would not be sufficient to establish efficacy for either the PROS or PS patients. As a consequence, Amendment 7 was written to remove all efficacy assessments, including the volumetric MRIs for the PROS patients, the CCTN photography for the PS patients, as well as to remove the functional assessments, among others.

# 2.3 Study Endpoints

Under this amendment, the endpoints for Part A and Part B have been combined to assess the safety and tolerability of miransertib in participants with PROS and PS based on the frequency, duration, and severity of AEs from the first dose of the drug through 90 days after the last dose of the drug.

#### 3 SELECTION OF STUDY POPULATION

Participants with PROS or PS with a documented PIK3CA or AKT1 somatic mutation will be enrolled in this study. It is expected that the study will be conducted at up to 10 sites globally. Part A is closed to enrollment. Part B will enroll approximately 65 participants. Participant accrual will occur over a period of approximately 24 months.

Participants must meet ALL of the inclusion criteria and NONE of the exclusion criteria to be enrolled.

#### 3.1 Inclusion Criteria

Part A is closed to enrollment after the approval of Amendment 6. See Annex 1 for inclusion/exclusion criteria for Part A.

#### 3.1.1 Part B:

1. Signed informed consent, and when applicable, signed assent

# 2. Cohort 1 (PROS) specific criteria

- Male or female participants ≥2 years and ≤30 years of age with BSA of ≥0.33 m^2.
   Participants should meet the age criterion by/on the date of the first dose Cycle 1 Day 1.
- Have clinical diagnosis of PROS per Diagnostic Criteria for PROS (Appendix 1) and documented somatic PIK3CA variant.
- Have at least one lesion that can be accurately measured by study-standardized volumetric MRI (eligibility to be confirmed by blinded central imaging review).

# 3. Cohort 2 (PS) specific criteria

- Male or female participants ≥2 years and ≤18 years of age with BSA of ≥0.33 m^2.
   Participants should meet the age criterion by/on the date of the first dose Cycle 1 Day 1.
- Have clinical diagnosis of PS per Diagnostic Criteria for PS (Appendix 1) and documented somatic AKT1 variant.
- Have at least one plantar CCTN and pre-CCTN lesion that can accurately be measured by standardized photography. The CCTN is defined as a nevus with at least 2 gyri and 3 sulci and should affect between 10% and 70% of the total surface area of the foot (eligibility to be confirmed by blinded independent central photo review).

# 4. Cohort 3 specific criteria

• Male or female PROS or PS patients  $\ge 2$  years old with BSA of  $\ge 0.33$  m^2 and who fail to meet the eligibility criteria for Cohorts 1 or 2. Participants should meet the age criterion by/on the date of the first dose Cycle 1 Day 1.

# 5. Cohort 4 (PROS or PS) specific criteria

- Participants previously treated with miransertib or currently receiving miransertib under Compassionate Use/Expanded Access
- 6. Archival or fresh overgrowth tissue sample available to be shipped to Sponsor or designee
- 7. Except for Cohort 4, clinically progressive or worsening disease defined as an increase in number or size of the overgrowth lesion(s) in the last 6 months as assessed by the investigator
- 8. Adequate organ function as indicated by the following laboratory values:
  - a. Hematological
    - 1. Hgb depending on age:
      - 2 to 5 years male and female:  $\geq 10.0 \text{ g/dL}$
      - 6 to 9 years male and female:  $\geq 11.5$  g/dL
      - 10 to 17 years female:  $\geq$ 11.0 g/dL
      - 10 to 17 years male:  $\geq$ 11.5 g/dL
      - $\geq$ 18 years male and female:  $\geq$ 10.0 g/dL
    - 2. HbA1c: ≤8% (≤64 mmol/mol)

- 3. ANC:  $\geq 1.5 \times 10^9/L$
- 4. Platelet count  $> 150 \cdot 10^9 / L$
- b. Hepatic
  - 1. Total bilirubin ≤1.5 x ULN
  - 2. AST and ALT  $\leq 3 \times ULN$
- c. Renal
  - 1. Serum creatinine depending on age:
    - 2 to 5 years male and female: maximum 0.80 mg/dL
    - 6 to 10 years male and female: maximum 1.0 mg/dL
    - 11 to 15 years male and female: maximum 1.2 mg/dL
    - >15 years male and female: maximum 1.5 mg/dL
  - 2. Estimated glomerular filtration rate (eGFR) ≥60 mL/min/1.73 m^2
- d. Metabolic (lipids)
  - 1. Cholesterol:  $\leq 400 \text{ mg/dL}$  ( $\leq 10.34 \text{ mmol/L}$ )
  - 2. Triglyceride: ≤500 mg/dL (≤5.7 mmol/L)
- 9. Male or female participants of child-producing potential must agree to use double-barrier contraceptive measures, oral contraception, or avoidance of intercourse during the study and for 90 days after the last dose of miransertib
- 10. Ability to complete the study questionnaires by the participant or his/her caregiver

#### 3.2 Exclusion Criteria – Part B

- 1. History of Type 1 diabetes mellitus or Type 2 uncontrolled diabetes mellitus requiring regular medication (other than metformin or other oral hypoglycemic agents) or fasting glucose ≥160 mg/dL (>12 years old) and ≥180 mg/dL (if ≤12 years old) at the Screening Visit
- 2. History of significant cardiac disorders
- 3. MI or congestive heart failure defined as Class II to IV per the NYHA classification within 6 months of the first dose of miransertib (MI occurring >6 months of the first dose of miransertib will be permitted)

#### PROTOCOL/AMENDMENT NO.: 002-07

- 4. Grade 2 (per current version of NCI CTCAE) or worse conduction defect (eg, right or left bundle branch block)
- 5. Major surgical procedures or locoregional therapy within 4 weeks of the first dose of miransertib
- 6. Any experimental systemic therapy for the purposes of treating PROS or PS (eg, sirolimus, everolimus, high dose steroids) within 2 weeks of the first dose of miransertib
- 7. Intolerance of or severe toxicity attributed to AKT inhibitors (eg, miransertib, uprosertib, afuresertib, ipatasertib)
- 8. Concurrent severe uncontrolled illness not related to PROS or PS, including:
  - Ongoing or active infection
  - Known HIV infection
  - Malabsorption syndrome
  - Psychiatric illness/substance abuse/social situation that would limit compliance with study requirements
- 9. Pregnant or breastfeeding
- 10. Inability to comply with study evaluations or to follow drug administration guidelines

#### 4 STUDY VISITS

Before the start of any study required procedures, the investigator or designee must obtain a signed written ICF and, when applicable, signed assent for the study from each prospective participant or his/her parent or legal guardian.

For Part A, all ongoing participants will continue treatment and will follow the Schedule of Events in Annex 1.

For Part B Cohorts 1, 2 and 3, study visits will consist of a Screening Visit, (during which the participant's eligibility for the study and baseline disease state will be evaluated), 2 visits during the first and fourth cycles, one visit per cycle for Cycles 2 and 3, and 5, then once every 2 cycles for Visits 7, 9, 11, and 13, and then one visit per every 3 cycles until EOT, during which the participant's clinical status will be evaluated, and a 30-Day Safety Follow-up (Table 3).

For participants enrolled in Cohort 4, study visits will consist of a Screening Visit, (during which the participant's eligibility for the study and baseline disease state will be evaluated), Cycle 1 Day 1 visit and then one visit per every 3 cycles (eg, Cycle 4 Day 1, Cycle 7 Day 1,

Cycle 10 Day 1, Cycle 13 Day 1, etc.) until EOT, during which the participant's clinical status will be evaluated, and a 30-Day Safety Follow-up (Table 4).

After the Screening Visit and a determination by the investigator and with Sponsor approval that the participant meets all inclusion criteria and none of the exclusion criteria, the participant will be considered entered into the study.

Participants enrolled in Part B, Cohorts 1 and 2, must also meet eligibility requirements according to applicable central imaging criteria.

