#### 4.1 Informed Consent

A sample ICF and Assent Form with core information will be provided to each study site. Before study initiation at a given study site, each site/investigator must obtain a written approval/favorable opinion from its respective IRB/IEC for the ICF, assent form, and any other written information to be provided to participants. All ICFs and assent forms must be compliant with the ICH GCP guidelines and local regulations and must be approved by the Sponsor before submission to the IRB/IEC. The written approval of the IRB/IEC, together with the approved participant information, ICF, and assent forms, must be maintained in the study master files.

Written informed consent and/or assent must be obtained from a prospective participant and his/her parent/legal guardian before any study-specific procedures are performed on that individual. Participants who agree to participate in the study will sign the most recently approved ICF and/or Assent Form and will be provided with a copy of the fully executed document(s). The original, executed ICF and Assent Form will be maintained in the respective participant's clinical study file.

The ICF can be signed greater than 45 days before dosing and does not need to be re-signed before dosing unless specific reasons or local regulations apply (eg, a new consent version has been issued and approved by the IRB/IEC).

All screening imaging assessments must be performed within 21 days of C1D1, unless rescan by MRI or repeat photography is required.

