**Table 4 Schedule of Events Part B Cohort 4** 

Phase	Screening	1	Гreatment (	(year 1)	Treatment (years 2	Follow-Up	
Tests & Procedures / Visit Name	Screening	C1	C4	C7, C10, C13	C16, C19, C22, C25, C28, C31, C34, C37, C40, C43, C46	EOT (C48)	30-day Safety Follow-up
Window (days)	-14 to 0	-1 to 0	± 5	± 5	± 5	Within 7 days	30+ Days
Written informed consent	X						
Medical history	X						
Physical examination	X	X	X	X	X	X	X
Vital Signs	X	X	X	X	X	X	X
Calculate BSA / dose		X	X	X	X		
12-Lead ECG		X	X			X	X
Fasting clinical blood tests	X		X	X	X	X	X
Insulin/glucose blood tests	X			X	X (C19, C25, C37)	X	
Urinalysis	X		X	X	X	X	X
Serum pregnancy test (if applicable)	X					X	X
Tissue biopsy	X						
Blood for CYP2D6		X					
Lesion measurement by imaging (e.g. DXA)	X						
Dispense miransertib 		X	X	X	X		
Collect and count returned miransertib capsules			X	X	X	X	
Concomitant medications	X	X	X	X	X	X	X
Adverse events		X	X	X	X	X	X

BSA=body surface area; C=cycle; DXA=dual-energy X-ray absorptiometry ECG=electrocardiogram; EOT=end of treatment.

Dispense 3-month allotments from C1 through C43; dispense 2-month allotment at C46.

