#### 8 ASSESSMENT OF RESPONSE

Efficacy assessments are no longer being conducted in this protocol with the adoption of Amendment 7. Analyses of previously collected responses may be performed by the Sponsor.

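### Amendment 7 drops MRI and photography, but Part B still asks for centrally reviewed screening imaging in Cohorts 1-2, an unused lesion image in Cohort 4, and ability to complete unscheduled questionnaires

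*Protocol*

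**What the plan says.** On removal, Protocol Section 2.2 states that "Amendment 7 was written to remove all efficacy assessments, including the volumetric MRIs for the PROS patients, the CCTN photography for the PS patients", and adds the functional assessments to the list. Section 8 agrees: "Efficacy assessments are no longer being conducted in this protocol with the adoption of Amendment 7". Section 2.1 leaves safety and tolerability as the only primary objective and says that final enrolment will be completed under Amendment 7, so the entry criteria may still be in use.

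On what remains:

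- **Cohort 1 (Section 3.1.1).** A lesion measurable on volumetric MRI, with "eligibility to be confirmed by blinded central imaging review".
- **Cohort 2 (Section 3.1.1).** A plantar CCTN and pre-CCTN lesion measurable on photographs, with "eligibility to be confirmed by blinded independent central photo review".
- **Section 4.** Participants in these two cohorts "must also meet eligibility requirements according to applicable central imaging criteria".
- **Section 4.1.** "All screening imaging assessments must be performed within 21 days of C1D1", with an exception where an MRI rescan or repeat photograph is needed.
- **Table 4 (Cohort 4).** A row beginning "Lesion measurement by imaging (e.g. DXA" is marked at Screening and nowhere else.
- **All Part B cohorts (Section 3.1.1, item 10, and the synopsis).** "Ability to complete the study questionnaires by the participant or his/her caregiver".

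Table 3, which covers Cohorts 1-3, has no row for MRI, photography, any lesion image or any questionnaire. Table 4 has no questionnaire row either.

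**The concern.** The protocol gives two instructions on the same procedures. One part says MRI and photography have gone because efficacy is no longer studied. Another makes them a condition of entry to two cohorts, with blinded central review. A site reading Section 2.2 and Table 3 would not order the image; a site reading Sections 3.1.1, 4 and 4.1 would.

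Two things are at stake. The first is burden: Cohorts 1 and 2 admit children from 2 years of age, and a new image taken only at screening has no stated use in a safety study. The second is consistency between sites, because cohort is a reporting stratum in both documents. The questionnaire criterion is a smaller matter of the same kind: it tests ability to do something that the schedules no longer ask anyone to do.

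**Working it through.** No arithmetic underlies the main point. The check is to ask, for each retained item, whether the current text requires it, schedules it and uses it.

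| Item | Required for entry? | Scheduled? | Used in an endpoint or SAP analysis? |
|---|---|---|---|
| Cohort 1 volumetric MRI with central review | Yes (3.1.1, 4, 4.1) | No row in Table 3 | No |
| Cohort 2 CCTN photography with central review | Yes (3.1.1, 4, 4.1) | No row in Table 3 | No |
| Cohort 4 lesion image | No criterion needs it | Screening only (Table 4) | No |
| Ability to complete questionnaires | Yes, all Part B cohorts | No questionnaire in Table 3 or 4 | No |

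**Use of the image.** The combined endpoint in Section 2.3 rests on adverse events. SAP Section 4.10 lists the baseline disease characteristics to be tabulated: life stage at which overgrowth was reported, family history, diagnosis and time since diagnosis. No lesion measurement is among them, and no other SAP section analyses imaging. Section 8 lets the sponsor analyse response data already in hand, but a new screening image is not that. Part B schedules no later image for comparison. If disease history is wanted, Section 5.1 already collects existing scans and photographs where they are available, without a new procedure.

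**Cohort 4.** Its specific criterion concerns past or current miransertib treatment. The general criterion on growth of lesions over the last 6 months exempts Cohort 4. Nothing in its eligibility depends on a lesion image.

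**What the image decides in Cohorts 1-2.** Section 6.3 gives Cohorts 1, 2 and 3 the same dosing, and Table 3 gives them the same visits. Cohort 3 is defined as patients who do not qualify for Cohort 1 or 2. Imaging therefore decides a cohort label and nothing else. Read literally, a patient who meets the other Cohort 1 or 2 criteria would have to be imaged even to be placed in Cohort 3.

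**Size.** Protocol Section 2.2 plans 20 in Cohort 1, 10 in Cohort 2, about 25 in Cohort 3 and about 65 in all. Subtraction leaves 65 − 20 − 10 − 25 = 10 for Cohort 4, which matches SAP Section 2.3. The imaging items thus attach directly to 20 + 10 + 10 = 40 planned places, and the questionnaire item to all 65. These are planned totals, not numbers outstanding. The synopsis describes the cohorts in the past tense, while Sections 2 and 2.2 use the future tense. The number left to enrol is not given.

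**The case against.** **Baseline imaging may have been kept on purpose.** The amendment summary gives on-treatment MRI for efficacy comparison as its example of what to remove. Section 4 says screening evaluates baseline disease state. Table 4's example is DXA, which is neither of the two modalities that Section 2.2 names. A baseline image might also help an investigator judge whether the disease has accelerated, which is a discontinuation criterion in Section 4.2.1. This is possible, but no section says so. That criterion rests on the investigator's opinion, and no follow-up image is scheduled. If there is a purpose, it needs stating and the image needs a row in Table 3.

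**A reader might infer that Cohort 1-2 eligibility cannot be established by following the schedule.** The documents do not support that. Table 3 refers the reader to other sections, and Section 4.1 supplies the imaging window. Table 3 is also visibly incomplete: it lacks rows for the tissue sample and the CYP2D6 blood sample, which the text requires for all participants. The missing imaging row makes the instructions inconsistent but does not prove them unworkable.

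**A reader might infer that patients are being shut out of the trial by imaging.** They are not, because Cohort 3 takes them. The questionnaire criterion could in principle exclude someone from Part B, but a caregiver's ability is enough to meet it, so that would be rare.

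**Redefining cohorts has a price.** Protocol Section 9.1 and SAP Section 4.4 report by Part, Cohort and overall, with adverse events also by dose within cohort. Changing the Cohort 1-2 boundary for the last entrants would mix definitions in those tables. This stands, and the fix allows for it.

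**Conclusion.** The inconsistency is real and sits in the current text. Screening imaging with central review remains an entry condition for Cohorts 1-2 after the protocol says those assessments were removed. Cohort 4 keeps a lesion image that nothing uses, and all Part B cohorts keep a criterion about questionnaires that are no longer scheduled.

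The consequence is limited to avoidable imaging and conflicting site instructions for anyone still to be enrolled. That number is unknown: it may be zero for Cohorts 1-2, and the 40 planned places with an imaging item should not be read as 40 people affected. The safety population and the pooled safety endpoint are unchanged, and cohort assignment bears only on the by-cohort tables.

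The conclusion assumes that some enrolment remained under Amendment 7, as Section 2.1 implies, and that no unstated purpose exists for the screening images.

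**What to change.** Reconcile Sections 3.1.1, 4 and 4.1, Tables 3 and 4 and the synopsis with Section 2.2. For participants entering under Amendment 7:

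1. Delete the lesion-imaging row from Table 4.
2. Delete the questionnaire criterion from Section 3.1.1 and the synopsis.
3. State that no new MRI, photograph or central review is required solely to assign a cohort.
4. Then choose one of two routes for Cohorts 1-2:
   - state that they are closed to enrolment and keep the imaging criteria only as a record of how their members were selected; or
   - drop the imaging criteria and the 21-day window for new entrants, and footnote the changed cohort definition in the by-cohort tables.

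Closing the cohorts is the cleaner route if they are already full, because it leaves the reporting strata intact. Dropping the criteria brings a small inconsistency in cohort definition.

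The change is to wording, but it is not free. Section 10.2 requires written IRB/IEC approval and, where applicable, approval by the authorities. If the consent form is updated and re-approved, Section 10.3 requires active participants to be reconsented. Against that, any remaining imaging and central-review work is saved.
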